## 2. OBJECTIVES

### a. Primary Objective

b. Primary outcome is to assess the difference between patients using remote monitoring and patients not using remote monitoring in perceived quality of recovery measured with the QoR-15 questionnaire on the 7th day after day care surgery.

### c. Secondary Objective(s)

To assess the experienced postoperative pain (POP) between patients provided with a smartphone application for remote monitoring and patients receiving standard of care (no remote monitoring) after day care surgery.

To assess the experienced post discharge nausea and vomiting (PDNV) between patients provided with a smartphone application for remote monitoring and patients receiving standard of care (no remote monitoring) after day care surgery.

To assess the difference in the number of surgical complications rated with the Clavien Dindo classification of surgical complication between patients provided with a smartphone application for remote monitoring and patients receiving standard of care (no remote monitoring) after day care surgery.

To assess the difference in the number of re-admissions between patients provided with a smartphone application for remote monitoring and patients receiving standard of care (no remote monitoring) after day care surgery.

To assess the difference in the number of hospital contacts / general practitioner between patients provided with a smartphone application for remote monitoring and patients receiving standard of care (no remote monitoring) after day care surgery.

To assess the difference in experienced quality of communication with the hospital staff between patients provided with a smartphone application for remote monitoring and patients receiving standard of care (no remote monitoring) after day care surgery.

To assess the experienced psychological effects remote monitoring in patients recovering from day care surgery

### 3. STUDY DESIGN

A two-arm multicenter non-blinded randomized controlled trial with mixed methods design will be conducted at the day care nursing wards of OLVG Hospital (Locations Oosterpark and Jan Tooropstraat), Amsterdam, the Netherlands, Canisius Wilhelmina Hospital, Nijmegen, the Netherlands and Maasstad Hospital, Rotterdam, the Netherlands. Surgical specialisms involved are gynecology, eye-nose and throat, oral and maxillofacial, orthopedics, general and vascular, trauma and urology. Surgical day care patients will be randomly assigned to one of the two study arms, remote monitoring with a smartphone application (intervention) or standard of care (no remote monitoring) after hospital discharge. Study period is expected to run from 1st of February 2022 up to the 31st December 2022.

#### **STUDY POPULATION**

##### **a. Population (base)**

For this study, we will enrol 230 consecutive patients admitted to OLVG Hospital, Canisius Wilhelmina Hospital or Maasstad Hospital who are scheduled to undergo a surgical intervention in day care. In 2020 under the pressure of the covid-19 pandemic over 8000 day care surgical interventions were performed therefore, it is likely that the inclusion will be achieved within the intended study period.

##### **b. Inclusion criteria**

In order to be eligible to participate in this study, a subject must meet all of the following criteria:

- Age: older than or equal to 18 years
- Pre-anaesthesia conclusion: ASA I to III
- Scheduled for day care surgery for one of the following surgical specialties:  
gynaecology, eye-nose and throat, oral and maxillofacial, orthopaedics, general and vascular, trauma and urology
  -
- In possession of a smartphone

##### **c. Exclusion criteria**

A potential subject who meets any of the following criteria will be excluded from participation in this study:

- Not able to speak or understand the Dutch language
- Mentally impaired (e.g. dementia, retardation)

During study:

- Patients who experience a unexpected post-operative complication or prolonged recovery with the result that discharge on the same day of the surgical intervention is not possible will be excluded

**d. Sample size calculation**

An 8.0 difference in the overall score in the QoR-15 questionnaire on postoperative day 7 is considered a minimal clinically relevant difference (16) with standard deviation of 19.1 (17). Group sample sizes of 91 patients achieve 80% power to detect a difference of -8.0 with a significance level (alpha) of 0,05 using a two-sided two-sample t-test. *Sample Size calculation is performed with PASS 2021 Power Analysis and Sample Size Software (2021). NCSS, LLC. Kaysville, Utah, USA, [ncss.com/software/pass](http://ncss.com/software/pass).* We plan to include 20% extra patients to adjust for dropout or incomplete data. Total sample will be 230 subjects divided into two groups.

## 4. TREATMENT OF PATIENTS

### a. Investigational product/treatment

Patients scheduled for day care surgery within 3 weeks after their pre-anaesthesia workup who fit the inclusion criteria and are willing to participate in this study are allocated to either remote monitoring with a smartphone application after discharge (the intervention) or the standard of care without remote monitoring (control). Both groups will have a pre-anaesthesia workup (e.g. online-assessment, telephone assessment or an assessment during a physical visit to the anaesthesia outpatient department) according to the standards of the Dutch association of Anaesthesiologist and Federation of Medical Specialists (18).

During the pre-anaesthesia workup, patients are being notified about the study by an anaesthesiologist, physician assistant or medical assistant. If interested they will receive the study information and a consent letter. Two days before admission a researcher will explain the study during a telephone call and will ask for informed consent. Moreover, participating patients are asked to complete the first online QoR-15 questionnaire.

Patients allocated to the intervention group also receive an invitation e-mail with instructions from Thuismeten (Luscii) © to download and install the remote monitoring application. This invitation is sent by a healthcare professional through a secured connection via the hospitals' patient data management system (e.g. EPIC ©). During the admission patients from both groups receive perioperative anaesthesia care according to standards based on the Guidelines for treatment of the Dutch association of anaesthesiologists (18, 19).

Patients are regularly asked about their postoperative pain and nausea by either nurses or doctors, at least once per perioperative phase (e.g. recovery and day care ward). In case of severe pain, the patient is administered paracetamol, NSAID's, tramadol or opioids. In case of nausea, the patient is administered metoclopramide or granisteron. Both, pain- and nausea treatment is executed by nurses with the aim of making the patient feel comfortable. Postoperative medication is ordered and supervised by the attending anaesthetist.

Before discharge, patients from both groups receive verbal and paper (APPENDIX I: example discharge information OLVG, in Dutch) care- and recovery instructions from a day care ward nurse. In addition, they receive a medication box containing paracetamol,

non-steroid inflammatory drug (NSAID), metoclopramide, pantoprazole and if they underwent a surgical procedure with intermediate risk for complications, they also receive tramadol or opioids.

In addition to standard care as delineated above, patients in the intervention group (remote monitoring after discharge) will have the monitoring application installed on their personal smartphone. Once they are back home, they can start recording pain and nausea and may ask questions about their recovery within the application. Once a day patients receive a push notification to record pain and nausea. The application is operational up to 7 days post discharge. After this period the application is disconnected from the Thuismeten (Luscii) © server.

In case of recording unbearable pain and nausea or asking a question and being in need for help or assistance, an anaesthesia medical assistant will contact these patients during office hours from 08:00 to 16:30 by using the applications' messaging service or by telephone. First the medical assistant will perform an initial triage of the patients in need, subsequently pain and nausea reports and additional questions that appear as an alert in the electronic back office systems of Thuismeten (Luscii) © will be addressed. The alerts are set to the in-app question 'do you want something to be done about your pain or nausea?' or an increase of 3 points numerical rating scale (NRS) for pain and additional questions asked in the apps messaging service. During triage, the medical assistant will follow a protocolled workflow to assess actions to be taken (APPENDIX II triage workflow, in Dutch). If contacting the patient by telephone is necessary, the medical assistant will use a call script to assess patients' pain, nausea and physical status (APPENDIX III, call script, in Dutch). The medical assistant will often give appropriate feedback or advice via message or telephone. In case of a possible medical alert or a necessary medication adjustment, the medical assistant will consult the anaesthetist, trainee nurse specialist or physician assistant responsible for remote postoperative pain care.

**b. Use of co-intervention (if applicable)**

Not applicable

**c. Escape medication (if applicable)**

Not applicable

**5. INVESTIGATIONAL PRODUCT (Not applicable)****a. Name and description of investigational product(s)**

Not applicable

**b. Summary of findings from non-clinical studies**

Not applicable

**c. Summary of findings from clinical studies**

Not applicable

**d. Summary of known and potential risks and benefits**

Not applicable

**e. Description and justification of route of administration and dosage**

Not applicable

**f. Dosages, dosage modifications and method of administration**

Not applicable

**g. Preparation and labelling of Investigational Medicinal Product**

Not applicable

**h. Drug accountability**

Not applicable

## 6. NON-INVESTIGATIONAL PRODUCT

### a. Name and description of non-investigational product(s)

The remote monitoring application for day care patients is a configuration of an already existing and applied monitoring platform by Luscii Healthtech B.V. The configuration for postoperative monitoring was commissioned by OLVG hospital. In this study app versions 2.43.0 or higher are being used. The application is CE IIa certified. For more information about Luscii technical, privacy and security specifications, we refer to

<https://www.notion.so/Security-and-privacy-at-Luscii-fc51e66e21ae4a87a51499a52d4c8db2>.

Information on intended use is available at <https://www.notion.so/luscii/Luscii-vitals-Instructions-for-Use-for-Patients-and-Clinicians-3d5050d94f6f40f9aa6af2e9aa77084d> both the triage protocol and the call script are developed by the OLVG hospital department of anaesthesia (APPENDIX II and III).

### b. Summary of findings from non-clinical studies

Not applicable

### c. Summary of findings from clinical studies

The Luscii tele-monitoring platform is currently being used in the care for patients with acute and chronic diseases such as hypertension during pregnancy, heart failure, COPD and COVID-19. The different telemonitoring modules are based on a direct feedback loop between patients and health care providers and alarming combinations of patient recorded results (20, 21). Results show a significant reduction of hospital admissions, days spent in hospital and healthcare costs (22, 23).

### d. Summary of known and potential risks and benefits

No potential risk or harm is to be expected from using the Luscii application and remote monitoring. Patients using the application and remote monitoring could benefit from being monitored daily by an anaesthesia medical assistant as formulated in the study objectives. It is expected that in patients receiving remote monitoring the quality of recovery be improved.

### e. Description and justification of route of administration and dosage

Not applicable

### f. Dosages, dosage modifications and method of administration

Not applicable

### g. Preparation and labelling of Non Investigational Medicinal Product

Not applicable

**h. Drug accountability**

Not applicable

## 7. METHODS

### a. Study parameters/endpoints

#### i. Main study parameter/endpoint

Quality of recovery measured with the Quality of Recovery questionnaire-15 (QoR-15) (16, 24) at day 7 post discharge between patients with remote monitoring (intervention group) and patients without remote monitoring (non-intervention group) after day care surgery.

#### ii. Secondary study parameters/endpoints (if applicable)

Quality of recovery measured with the quality of recovery questionnaire-15 (QoR-15) (16, 24) at post discharge day at post discharge day 1, 4 and 7.

Postoperative Pain: Experienced postoperative pain (POP) measured with (in-app) NRS for Pain (25) (combined with 11 faces scale) measured at day 1, 4 and 7 post discharge.

Post discharge nausea and vomiting: Experienced post discharge nausea and vomiting (PDNV) measured with the Myles' PDNV assessment scale (21) between intervention and non-intervention group. Measured at day 1, 4 and 7 post discharge.

Medication Dosage and Use: the total dosage of administered analgesics will be assessed during hospital stay and recorded in the medical record. The total dosage of administered analgesics at home after discharge will be assessed by asking patients to indicate which pain medication they have been using. Measured at day 1, 4 and 7 post discharge.

The number of contacts with the hospital, general practitioner or emergency department. All types of contacts (e.g. physically, e-mail, telephone) will be assessed by reviewing the PDMS for registered contacts and by asking the patients to indicate the number of contacts.

Measured at day 1, 4 and 7 post discharge.

The number of surgical complications assessed according to the Clavien Dindo classification of surgical complications (26, 27) will be assessed by reviewing the PDMS and by asking the patients to indicate the number of complications. Measured at day 1, 4 and 7 post discharge.

The number of readmissions. A readmission is defined as an admission to hospital or emergency department for medical care or observation regarding their surgical intervention. Readmissions will be assessed by reviewing the PDMS and by asking the patient to indicate the number of readmissions. Measured at day 1, 4 and 7 post discharge.

Satisfaction: Patients' satisfaction with the provided care will be assessed using a 1-item self-created VAS scale ('not at all to very much', 0-10 range). Satisfaction will be measured at day 1, 4 and 7 post discharge.

General evaluations regarding provided care after discharge: Patients' evaluations of their experienced care during the 7 day discharge period are measured using two items. i) How likely is it that the patient would recommend this hospital to other day care surgery patients (using an adapted item from the CQ index (0-10 'would definitely not recommend' to 'would definitely recommend') (28, 29). ii) Their overall rating of the quality of care provided by the hospital during the 7 day discharge period, using an item from the CQ index (0-10 scale, 'very poor care' to extremely good care') (28, 29). Both items will be measured at discharge day 1, 4 and 7.

The quality, experiences and communication regarding remote monitoring with this application will be assessed in one by one semi structured interviews. The perceptions of 20 participants are considered satisfactory or when data saturation is reached (REF). Prior to the interview, participants receive general information concerning the topics and informed consent was requested from the interviewee to allow for audio recording of the interview. See for interview topics (f1\_Interview Topics\_version\_1\_11\_2021-). Furthermore, interviews are conducted by telephone or online through Skype, Zoom or FaceTime due to COVID-19 measures.

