care according to the standards of the Dutch association of anaesthesiologist (18, 19). Intra- and postoperative characteristics and variables will be recorded in Castor EDC by the researchers. Before discharge, patients from both groups receive verbal and paper care and recovery instructions from a day ward nurse. In addition patients receive a medication box with instructions for use, containing paracetamol, naproxen or diclofenac and in case of an intermediate surgical risk for complications also tramadol or an opioid. Once at home, patients in the intervention group can start using the smartphone application for recording pain and nausea and ask additional questions about their recovery. Subsequently an anaesthesia medical assistant will respond appropriately to patients in need following triage and assessment protocol. At day 1, 4 and 7 post discharge patients from both groups receive an online questionnaire (QoR-15). In case patients do not respond, a researcher or a medical assistant will contact the patients from both study arms by telephone to assess the study endpoint questionnaire (f1\_vragenlijst\_QuReMo\_English\_version\_1\_16\_7\_2021 ). Thereafter, endpoint data will be recorded in Castor EDC by one of the researchers.

In addition, patients from the remote monitoring group who have given permission for an interview to assess the quality of communication with app receive a telephone appointment at day 7 postoperative for a 30 minutes semi structured interview with one of the researchers.

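### The between-arm pain endpoint is defined by an in-app rating that only the intervention arm can give, and the source of the control arm's pain score is not stated

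*Combined protocol and SAP*

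**What the plan says.** Section 2c sets a between-arm pain objective: "To assess the experienced postoperative pain (POP) between patients provided with a smartphone application for remote monitoring and patients receiving standard of care". Section 7a.ii defines the measure. Pain is "measured with (in-app) NRS for Pain (25) (combined with 11 faces scale) measured at day 1, 4 and 7 post discharge", and no other post-discharge pain instrument or mode is named.

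Section 4a describes the app as an addition to standard care: "patients in the intervention group (remote monitoring after discharge) will have the monitoring application installed on their personal smartphone". In that arm, "Once a day patients receive a push notification to record pain and nausea". The same section lists what raises an alert to staff: the patient's answer to an in-app question on whether something should be done about pain or nausea, and "an increase of 3 points numerical rating scale (NRS) for pain and additional questions asked in the apps messaging service".

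Section 7c describes the data collection common to both arms: "At day 1, 4 and 7 post discharge patients from both groups receive an online questionnaire (QoR-15" in brackets as its only label. For non-responders, staff "contact the patients from both study arms by telephone to assess the study endpoint questionnaire", which is a separately named file that is not part of the documents.

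Section 9b analyses pain with a mixed model containing arm, time (before surgery and days 1, 4 and 7), their interaction and a random intercept per patient. Section 9d handles missing data by multiple imputation.

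**The concern.** A between-arm comparison needs the same measurement in both arms. Here the only written definition points to a device that one arm does not have. The app score is also more than a research rating. The patient is prompted for it daily, and a sufficient rise brings staff contact. A patient entering that number may be signalling for help, whereas a patient answering a research form is not.

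If app scores were used for one arm and something else for the other, the difference in mode and purpose would follow randomisation exactly. The model in Section 9b has no term for mode, and adding one would not help, because mode would be indistinguishable from arm. The resulting difference in pain could not be attributed to monitoring. The shift could go in either direction, so it could create an apparent effect or hide a real one.

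**Working it through.** **Step 1. Can the definition be applied in both arms?**

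| Question | Intervention arm | Control arm |
|---|---|---|
| Pain compared between arms (2c, 9b)? | Yes | Yes |
| Has the app (4a)? | Yes | No |
| Can give an in-app NRS on days 1, 4 and 7 (7a.ii)? | Yes | No |
| Receives the online questionnaire on days 1, 4 and 7 (7c)? | Yes | Yes |
| Pain NRS stated to be in that questionnaire? | Not stated | Not stated |
| Pain rating can raise an alert (4a)? | Yes, in the app | No app, so no |

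The definition can be carried out only in the intervention arm. The one route common to both arms is the questionnaire, and the text does not say that it contains a pain NRS.

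**Step 2. What follows under each possible source?**

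- *Pain NRS in the common questionnaire, and that score analysed.* The comparison is sound, but it is not the one Section 7a.ii defines.
- *Pain NRS in the common questionnaire, app score analysed for the intervention arm.* App patients have two scores on the same days. No rule chooses between them, and the written definition picks the app score. Mode and purpose then differ by arm.
- *No pain NRS in the common questionnaire.* Controls have no post-discharge value, the arm effect cannot be estimated, and multiple imputation has no observed control values to draw on.

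Section 7a.iii collects a preoperative NRS in all patients, and app recording starts once the patient is home (4a). If that preoperative score is the before-surgery measurement in the model, a mode shift that begins after discharge in one arm would fall on the arm-by-time interaction, the term meant to show the effect.

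**Step 3. Sample size inputs.** The plan gives no sample size, SD or power for pain, so only the primary calculation can be reproduced. The inputs from the sample size section are a difference of 8.0, SD 19.1, two-sided alpha 0.05 and power 80%. The noncentral t calculation gives n = 90.45, hence 91 per arm, with power 0.802. This agrees with the plan. Allowing for 20% dropout, 182 / 0.80 = 227.5, or 228, against 230 stated. The stated total is 230 / 2 = 115 per arm.

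**Step 4. Illustration of a mode shift.** Assume no true effect, a systematic shift of *d* standard deviations between modes, and a two-sided 0.05 t-test at one time point. The noncentrality is *d* × √(n/2).

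- n = 91, d = 0.1: 0.1 × √45.5 = 0.67, rejection 10%.
- n = 91, d = 0.2: 0.2 × √45.5 = 1.35, rejection 27%.
- n = 115, d = 0.1: 0.1 × √57.5 = 0.76, rejection 12%.
- n = 115, d = 0.2: 0.2 × √57.5 = 1.52, rejection 33%.

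The nominal rate is 5%. The values of *d* are assumptions, since the documents give no figure for a mode shift.

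**The case against.** The best reply is that the bracketed qualifier is loose wording and that a pain NRS sits in the questionnaire both arms receive. Several things support this. The pain endpoint is timed at days 1, 4 and 7, which is the questionnaire's schedule; the app prompts daily. Section 7a.ii lists other patient-reported items for the same days (analgesic use, contacts, complications, readmissions, satisfaction and care ratings) with no restriction to the app or to one arm, so the questionnaire very probably holds more than the QoR-15. The authors also plan a between-arm pain model, which would be pointless if controls had no values. It is also fair to say that an ordinary pain entry does not by itself bring staff contact; only the listed triggers do.

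Much of this stands. A reader might infer that control pain must be either missing or measured by a different mode. The documents do not support that: a common item is a live third possibility, and the file that would settle it is not available. A reader might also take the rejection rates above as the trial's error rate. They are not. They rest on assumed shifts and a single-time test, not on the planned mixed model.

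The reply does not remove the gap. Even if a common item exists, the written definition names the app score, and no rule says which of two scores is analysed. That choice would stay open until the data are in hand.

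**Conclusion.** The point holds in a limited form. A between-arm secondary endpoint is specified by an instrument available in one arm only, the control arm's source and mode are not stated, and no rule selects between two scores for app patients. Applied literally, the definition ties measurement mode and purpose to allocation. Whether the conduct of the trial would actually be biased cannot be determined from the documents, because it depends on the content of the endpoint questionnaire. The size of any bias is unknown. The 10% to 27% at 91 per arm (12% to 33% at 115) shows only that a small shift of 0.1 to 0.2 SD would matter.

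Pain is the first-listed secondary objective, so the gap should be closed before analysis. The primary QoR-15 endpoint does not depend on it.

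**What to change.** In Section 7a.ii, delete the bracketed in-app qualifier. State that the pain NRS for the between-arm analysis comes from the day 1, 4 and 7 questionnaire given to both arms, with the same wording, recall period and mode, and with the telephone back-up applied alike in both arms. Name that score as the outcome in the Section 9b pain model. State that in-app scores are used only for monitoring and for description within the intervention arm.

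If the questionnaire already has a pain NRS, the cost is one sentence. If it does not, add one short item to a form that both arms already complete.

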### b. Secondary study parameter(s)

Postoperative pain on post discharge day 1, 4 and 7: Mean, Standard Deviation, Mixed effects linear regression models will be conducted to investigate the effect of the smartphone app on postoperative pain over the first week post discharge as a function of the randomization assignment (i.e. intervention vs control), time (i.e. measurements before surgery, and at day 1, 4 and 7 post discharge), and their interaction term. Random effects, i.e. random intercept, will be fitted per individual to account for clustering effects

Post discharge Nausea and Vomiting (PDNV) on post discharge day 1, 4 and 7: Mean, Standard Deviation and Mixed effects linear regression models will be conducted to investigate the effect of the smartphone app on PDNV over the first week post discharge as a function of the randomization assignment (i.e. intervention vs control), time (i.e. measurements before surgery, and at day 1, 4 and 7 post discharge), and their interaction

term. Random effects, i.e. random intercept, will be fitted per individual to account for clustering effects

Medication Dosage and usage measured in morphine equivalents on post discharge day 1, 4 and 7: Mean, Standard Deviation and Mixed effects linear regression models will be conducted to investigate the effect of the smartphone app on medication dosage and usage over the first week post discharge as a function of the randomization assignment (i.e. intervention vs control), time (i.e. measurements before surgery, and at day 1, 4 and 7 post discharge), and their interaction term. Random effects, i.e. random intercept, will be fitted per individual to account for clustering effects

Difference in the number contacts with the hospital, general practitioner or emergency department (on day 7 post discharge): Mean and Standard Deviation and two sample-t-test (in case of non-normally distributed data we will report on medians and interquartile ranges and differences will be tested using the Mann-Whitney U test)

Difference in the number of surgical complications assessed according to the Clavien Dindo classification of surgical complications (on day 7 post discharge): Mean, Standard Deviation and two sample-t-test (in case of not normally distributed data we will use the Mann-Whitney U test)

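### Home analgesic use is defined as total dosage, but only drug identity is described as collected, and the morphine-equivalent unit leaves out the paracetamol and NSAID that every patient receives

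*Combined protocol and SAP*

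**What the plan says.** Four parts of the combined protocol and SAP bear on this endpoint.

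- **Definition (section 7a.ii, Medication Dosage and Use).** "The total dosage of administered analgesics at home after discharge will be assessed", and the method given is "by asking patients to indicate which pain medication they have been using", at days 1, 4 and 7 after discharge. In-hospital dosage is handled separately and comes from the medical record.
- **Analysis (section 9b).** The heading is "Medication Dosage and usage measured in morphine equivalents on post discharge day 1, 4 and 7". Means and standard deviations are reported, and a mixed effects linear regression with a random intercept per patient is fitted to "investigate the effect of the smartphone app on medication dosage and usage over the first week post discharge". No conversion source is named and there is no rule for non-opioids.
- **Supply (sections 4a and 7c).** In section 4a all patients receive paracetamol together with "non-steroid inflammatory drug (NSAID), metoclopramide, pantoprazole", and "if they underwent a surgical procedure with intermediate risk for complications, they also receive tramadol or opioids". Section 7c describes the box as "containing paracetamol, naproxen or diclofenac and in case of an intermediate surgical risk for complications also tramadol or an opioid".
- **Instrument and accountability.** Section 7c cites the endpoint questionnaire by file name; its items are not reproduced. Section 6h marks drug accountability as not applicable, so no tablet count is described as a second source of dose.

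**The concern.** The definition, the data described and the analysis unit do not match. The definition covers all analgesics and asks for a total dose. The described item gives drug identity. The analysis uses an opioid-only scale.

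The intervention could plausibly change home analgesic use. App alerts lead to triage, advice and, where needed, consultation about changing medication (section 4a). If patients in one arm take more or less paracetamol or NSAID, the planned analysis cannot show it, and a null result could be misreported as no effect on analgesic use. If amounts are in fact not being asked, later recall would be a poor substitute, so the gap is best closed before the questionnaires go out.

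**Working it through.** The plan gives no figure for this endpoint: no expected mean, standard deviation, conversion factor or share of patients supplied an opioid. There is nothing to reproduce, so the check sets the sections against one another.

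**1. What a morphine-equivalent value needs.** For one patient and one reporting window,

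M = sum over opioids k of (units taken of k × strength per unit of k × conversion factor of k).

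| Input | Provided by the documents? |
|---|---|
| Which drug k | Yes, patient report (7a.ii) |
| Units taken | Not described |
| Strength per unit | Not described |
| Recall window (last 24 hours, or since the previous questionnaire) | Not described |
| Conversion factor | Not given (9b) |

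On the text alone, M for home use cannot be formed. Loose phrasing is possible, but the same section asks patients for *the number of* contacts, complications and readmissions, and for analgesics asks *which*.

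**2. What the unit covers.** Paracetamol and NSAIDs are not opioids and do not enter the sum. Take two patients with no opioid. One uses no analgesic, and the other uses all the paracetamol and NSAID in the box. Both have M = 0. The two supply lists agree on the essential point: a non-opioid pair for everyone, and an opioid only for one procedure class. M therefore measures home opioid use, not the total that section 7a.ii defines. Collecting amounts would cure step 1 but not this.

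**3. What the distribution is likely to be.** If q is the proportion of patients taking any opioid in a reporting window, the proportion with M = 0 is 1 − q. The documents give neither q nor the proportion of intermediate-risk procedures, so 1 − q stays unquantified. Since opioids are supplied to one class only, and a patient supplied with one need not take it, many zeros are likely. A linear mixed model with normal residuals describes a cluster at zero with a right tail poorly. For contacts, complications and readmissions, section 9b names a rank test if the data are not normal; for medication it names no alternative.

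**4. What is not touched.** The primary endpoint is the QoR-15 at day 7. The sample size in the study population section rests on that score alone and does not depend on medication data.

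**The case against.** A reader might infer that the endpoint cannot be computed at all. The documents do not support that. The questionnaire is not shown, and one sentence in section 7a.ii need not list all its items. If it asks for amounts, opioid morphine equivalents can be computed once a conversion source is named, and zero is the correct value for a patient who took no opioid. In-hospital opioid dose has a source in any case. What stands is that the plan shows no home dose item, and that an opioid-only total is not the endpoint as defined.

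A reader might also take patients sent home without an opioid to be zero by design at every time point. That goes too far. Section 4a allows medication to be adjusted after triage, section 7a.ii counts contacts with general practitioners and emergency departments that might change analgesia, and a history of chronic pain is recorded (7a.iii) without being an exclusion, so patients may have their own supply. Zeros are likely, not structural, and no percentage can be attached to them. Nor do the documents show that advice acts mainly on paracetamol or NSAID use; the triage workflow and call script are appendices not shown.

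Finally, medication use is missing from the secondary objectives in section 2 and from the secondary endpoints in the summary. That limits the weight of the point, but section 9b still gives the endpoint a model of its own, so it should be analysable as defined.

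**Conclusion.** The point holds in a limited form. Section 7a.ii promises a total dose of home analgesics and describes collecting only drug identity. Section 9b analyses it on a scale that ignores the analgesics supplied to every patient, with a model poorly suited to the many zeros that are likely. The first part depends on the unseen questionnaire and would be settled by stating that amounts are asked. The unit and the model need changing either way.

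The size cannot be given as a number: the share of zeros is not stated, and no bias or loss of power has been calculated. The conclusion rests on morphine equivalents being applied to opioids only and on the supply rules in sections 4a and 7c being followed. It concerns one secondary endpoint and home use only. It should be corrected, but it does not threaten the primary result.

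**What to change.** 1. **Data (section 7a.ii and the questionnaire).** Confirm or add, for both arms at days 1, 4 and 7, the number and strength of units taken of each analgesic, whether from the box or another source, over a stated recall window. If the questionnaire already asks this, say so in section 7a.ii.
2. **Opioids (section 9b).** Name the conversion source. Analyse any opioid use (yes/no) and opioid morphine equivalents in all randomised patients, with a method suited to many zeros, such as an ordinal mixed model or a two-part model. In a two-part model, the comparison of amounts among users is descriptive, because use follows randomisation.
3. **Subgroup, if one is wanted.** Define it only by the procedure's risk class, fixed before discharge. Do not define it by who was later supplied an opioid, since the app may influence that. Section 7a.iii already records procedure and classification.
4. **Non-opioids (section 9b).** Report paracetamol and NSAID amounts separately, each on its own scale.

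The cost is a few more questionnaire fields for patients in both arms, revised wording in two sections, and somewhat more analysis work. No change to treatment is involved.
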